4.4.1 Management of Hypoglycemia

Hypoglycemia is a rare side effect of metformin in both diabetic and non-diabetic patients. All patients, however, will be warned of the potential signs and symptoms (i.e. hunger, headache, confusion, irritability, drowsiness, weakness, dizziness, tremors, sweating, fast heartbeat, seizure or fainting). If these symptoms were to occur, patients would be counseled to consume one of these quick-fix foods right away to raise their blood glucose.

- 3 or 4 glucose tablets
- 1 serving of glucose gel—the amount equal to 15 grams of carbohydrate
- 1/2 cup, or 4 ounces, of any fruit juice
- 1/2 cup, or 4 ounces, of a regular—not diet—soft drink
- 1 cup, or 8 ounces, of milk
- 5 or 6 pieces of hard candy
- 1 tablespoon of sugar or honey

After this, patients would be instructed to contact the gynecologic oncology clinic or study coordinator for further recommendations. If patients already have a glucose meter, patients would be counseled to check their glucose level immediately. If the level is below 70 mg/dL, one of the above quick-fix foods would be consumed right away to raise their blood glucose. Patients will be instructed to recheck their blood glucose in 15 minutes to make sure it is 70 mg/dL or above. If it is still too low, another serving of a quick-fix food should be eaten. These steps should be repeated until the blood glucose level is 70 mg/dL or above. As stated previously, hypoglycemia is less likely in non-diabetic patients. If this were to occur, they will be managed in the same manner as detailed above.

4.5 Concomitant Medications/Treatments

Patients are excluded if they are currently taking cimetidine. No other medications are absolutely contraindicated while on metformin therapy.

4.6 Other Modalities or Procedures

4.6.1 Endometrial Biopsies

Patients will undergo follow-up endometrial biopsies every 3 months to assess histology and grade and to determine disease persistence, response, or progression, as per standard of care. Metformin therapy will continue without change in dosing on biopsy days. At the 6 month time point only, an additional pass will be made with the endometrial pipelle, in order to collect tissue for the correlative studies.

These patients will already be familiar with the procedure of endometrial biopsy since most will have undergone this procedure when they were diagnosed. Endometrial biopsies will be performed either by a gynecologic oncology attending, gynecology attending, gynecology resident or gynecologic oncology clinical fellow. Patients will be offered acetaminophen or non-steroidal anti-inflammatory drugs (i.e. ibuprofen) if needed for uterine cramping. Patients will be given appropriate instruction on fever and bleeding precautions during the surgical procedure consent process.

An endometrial suction curette (e.g., Pipelle®) will be used to sample the endometrial lining for each follow up biopsy. These disposable devices are constructed of flexible polypropylene with an outer sheath measuring approximately 3 mm in diameter with a 2.4 mm distal side port, through which the endometrial sample is obtained. The flexibility of this type of curette allows the cannula to conform to the contour of the uterus and minimizes cramping. The accuracy of endometrial biopsy to detect endometrial disease, especially the sensitivity of detecting endometrial cancer is 83% to 96% (47-50).

The most common risks to the patient for this procedure are cramping and a vaso-vagal response. Other much rarer risks included uterine bleeding (usually due to previously undiagnosed coagulopathies), uterine perforation (0.1 – 1.3%), pelvic infection and bacteremia (<1%). Besides these risks, there are no known additional risks to patients undergoing multiple endometrial biopsies. These procedures would be performed regardless of study enrollment.

4.7 Duration of Metformin Therapy

The planned duration of metformin therapy is 12 months. Metformin treatment will be discontinued early in the following scenarios:

- Progression of disease, as defined by CAH progression to invasive adenocarcinoma or grade 1 EC progression to grade 2 or 3 EC, at any of the standard of care biopsies at 3, 6, and 9 months. In any of these cases, metformin will be discontinued within 3 days of results of the biopsy.
- Unacceptable toxicity as defined by a single grade 3 or higher GI disturbance attributed to metformin, a single grade 4 or higher hypoglycemia episode, 2 or more grade 2 toxicities attributed to metformin, or requirement for a dose below 850 mg once daily.

Response to therapy will be assessed at 3-month intervals. As per standard of care, endometrial biopsies will be performed every 3 months (+/- 2 weeks) to assess histology and grade to determine response. This will be the basis of whether therapy should continue. If the 3 month biopsy demonstrates disease progression, the patient will be removed from protocol directed treatment and followed-up per protocol, and treatment decisions will be at the discretion of the treating physician. Otherwise, therapy will continue through 6 months. If the 6-month or 9-month biopsy demonstrates complete response (complete disease regression) or partial response (partial disease regression), metformin will be continued until 12 months of total therapy is given. If the 6-month or 9-month biopsy demonstrates stable disease, continuation of metformin on study will be at the discretion of the treating physician. Please see the schema (section 4.1) for clarity.

In addition, treatment will be stopped in the setting of:

- Inter-current illness that prevents further administration of treatment
- Pregnancy
- Patient decides to withdraw from study treatment, **OR**
- General or specific changes in the patient's condition render the patient unacceptable for further treatment in the judgment of the investigator.

4.8 Duration of Follow Up

Patients will be followed until their final study encounter (this may be a clinic visit, or phone call), which will occur within 30 days of their final endometrial biopsy while on metformin. Metformin is to be stopped the day of the 12-month endometrial biopsy, or the day on which the results of prior biopsies are known, if they indicate disease progression. In the case of ongoing adverse events/serious adverse event, patients will be followed to resolution of the event.

4.9 Removal of Patients from Protocol Therapy

Patients will be removed from protocol therapy when any of the criteria listed in section 4.7 apply. The Principal Investigator will be notified, and the reason for study removal and the date the patient was removed will be documented in the electronic Case Report Form (e-CRF).

In case a patient decides to prematurely discontinue protocol therapy ("refuses treatment"), the patient should be asked if she may still be contacted for further scheduled study assessments. The outcome of that discussion should be documented in both the medical records and in the eCRF.

Excessive patient withdrawals from protocol therapy or from the study can render the study un-interpretable; therefore, unnecessary withdrawal of patients should be avoided.

4.10 Study Withdrawal

If a subject decides to withdraw from the study (and not just from protocol therapy) an effort should be made to complete and report study assessments as thoroughly as possible. At the time of withdrawal, the Investigator should attempt to establish as completely as possible the reason for the study withdrawal.

- The subject should be asked if they are willing to allow for the abstraction of relevant information from their medical record in order to meet the long term follow up (e.g., survival) objectives outlined in the protocol.
- A complete final evaluation at the time of the subject's study withdrawal should be obtained with an explanation of why the subject is withdrawing from the study.
- If the subject is noncompliant and does not return for an end of study follow up assessment, this should be documented in the eCRF.
- If the reason for removal of a subject from the study is an adverse event, the principal specific event will be recorded on the eCRF.

Excessive subject withdrawals from protocol therapy or from the study can render the study un-interpretable; therefore, unnecessary withdrawal of subjects should be avoided.

5.0 DRUG INFORMATION

5.1 Commercial Drug Description and Management -Metformin

5.1.1 Mechanism of Action/Indications

Metformin is an antihyperglycemic agent that improves glucose tolerance in patients with type II diabetes, lowering both basal and postprandial plasma glucose. Its pharmacologic mechanisms of action are different from other classes of oral antihyperglycemic agents. Metformin decreases hepatic glucose production, decreases intestinal absorption of glucose, and improves insulin sensitivity by increasing peripheral glucose uptake and utilization. Unlike sulfonylureas, metformin does not produce hypoglycemia in either patients with type II diabetes or normal subjects (except in special circumstances, see adverse events section) and does not cause hyperinsulinemia. With metformin therapy, insulin secretion remains unchanged while fasting insulin levels and day-long plasma insulin response may actually decrease.

5.1.2 Supplier/How Supplied

Metformin is generic and made by several different manufacturers. Investigational Drug Services at participating centers will be responsible for the purchase and distribution of metformin to the patients enrolled in this study. Patients will be provided metformin free of charge for this trial.

Clinical supplies will be affixed with a clinical label in accordance with regulatory requirements.

This trial is open-label; therefore, the subject, the trial site personnel, the Sponsor and/or designee are not blinded to treatment. Drug identity (name, strength) is included in the label text; random code/disclosure envelopes or lists are not provided.

5.1.3 Dosage and Administration

For type II diabetes mellitus, the initial recommended dosage of metformin is 500 mg twice daily or 850 mg once daily given with meals, and then titrated to twice daily dosing. For this study, patient will take 850 mg once daily, and this dose will be titrated to twice daily dosing. Metformin should be taken with meals.

5.1.4 Storage and Stability

Metformin should be stored between 20 and 25 degrees Celsius (68 and 77°F) with excursions permitted between 15 and 30°C (59 and 86°F). Metformin is dispensed in a light-resistant container.

5.1.5 Handling and Disposal

The investigator or designee is responsible for keeping accurate records of the clinical supplies received for this trial, the amount dispensed to and returned by the subjects, and the amount remaining at the conclusion of the trial.

Local requirements for disposal of hazardous drugs should be followed at each participating clinical site. Please see UNC policy on hazardous drugs:

<https://unchealthcare-uncmc.policystat.com/policy/4734545/latest/>

Full prescribing information for Metformin is available at:
https://packageinserts.bms.com/pi/pi_glucophage_xr.pdf

5.1.6 Adverse Events Associated with Metformin

The potential risks involved in metformin treatment are minimal but include gastrointestinal side effects, lactic acidosis, hepatotoxicity and hypoglycemia. All patients will have a serum pregnancy test (if of childbearing age) and baseline creatinine and liver enzymes drawn at the time of their enrollment. These labs will be reviewed by the principal investigator, and the patient notified that she has been cleared to take metformin per the inclusion/exclusion criteria. Patients will be contacted weekly during the first 2 weeks of metformin treatment and then every 30 days by the study coordinator to ensure that these women are not experiencing any appreciable side effects.

Hypoglycemia is a rare side effect of metformin in both diabetic and non-diabetic patients. See section 4.4.1 for information on management of hypoglycemia.

Please refer to the agent's package insert for a comprehensive list of adverse events.

5.2 Commercial Drug Description and Management- Levonorgestrel-Releasing Intrauterine Device

Mechanism of Action and Indications

The LR-IUD is commercially available as the Mirena© intrauterine system. It is a sterile T-shaped polyethylene frame with a steroid reservoir containing 52 mg of levonorgestrel. It is a long-term contraceptive agent and used to treat heavy menstrual bleeding. The mechanism of action that prevent pregnancy include thickening of the cervical mucus, inhibition of sperm capacitation, and alterations of the endometrium. The alterations of the endometrium are a result of local progestin effects and include stromal pseudodecidualization, glandular atrophy, a leukocytic infiltration and a decrease in glandular and stromal mitoses. Due to these effects, the LR-IUD has been used in diseases previously treated with oral progestin therapy - heavy menstrual bleeding and hyperplasia and early endometrial adenocarcinoma.

Supplier/How Supplied

The LR-IUD is currently only commercially available in the Mirena© intrauterine system. As a standard alternative treatment for hyperplasia and early stage endometrial adenocarcinoma, it is reimbursed by insurance plans and will be supplied by the UNC pharmacy. Patients and/or their insurance companies will be billed for this product.

Formulation/Dosage and Administration

The LR-IUD contains 52 mg total of levonorgestrel and releases approximately 20 mcg/day.

Storage/Stability

Mirena© is supplied sterile and is sterilized with ethylene oxide. It is stored at 25°C with excursions permitted between 15-30°C. If the package seal is disrupted prior to use, it must be discarded. It cannot be re-sterilized.

5.3 Adverse Events Associated with Commercial Drug

The most common adverse reactions associated with the LR-IUD is change in menstrual bleeding pattern, abdominal/pelvic pain, and the formation of headache/migraines. As part of standard therapy, patients would be counseled about these possible effects. They will be instructed to call the gynecologic oncology clinic if any concerns arise.

The majority of LR-IUD users experience resolution of such symptoms between 1 – 12 weeks after insertion. In the setting of changes in bleeding pattern, this is most commonly a decrease in heavy bleeding associated with CAH/EC and would be unlikely to require intervention. Abdominal/pelvic pain will be treated with

non-steroidal anti-inflammatory medication or acetaminophen as needed, in over the counter formulations. Headaches and/or migraines that result from the LR-IUD will be similarly treated with non-steroidal anti-inflammatory medication or acetaminophen. Persistent headaches requiring discontinuation of the LR-IUD would be addressed by the primary physician as this would impact standard of care therapy for inoperable CAH/EC.

Pregnancy. Pregnancy is rare with the LR-IUD, with a reported rate of 0.1% for ectopic pregnancy. There have been 390 live births out of 9.9 million LR-IUD users as of 2006.

Uterine Perforation. At the time of placement of the LR-IUD there is a risk of uterine perforation. Correct technique by trained personnel mitigates most of this risk. Perforation can be recognized at the time of insertion or at any time when the cervical os strings are no longer visible. Pregnancy may occur in this setting.

Expulsion. The highest rate of expulsion occurs in the first month after LR-IUD placement and can be up to 4.9%. Risk factors for expulsion include placement by untrained personnel and recent (<6 weeks) pregnancy or abortion.

Please see the package insert for a comprehensive list of adverse events.

6.0 EVALUATIONS AND ASSESSMENTS

6.1 Time and Events Table

	Screening	Pre-treatment Visit	Month (Mo) 1 Week (Wk) 1	Mo3	Mo6	Mo9	Mo12	Early Termination ²	Final Study Encounter ²
Inclusion/ Exclusion Criteria	X								
History ¹ and Physical	X			X	X	X	X		
Informed Consent	X								
Education of potential side effects		X							
Pregnancy test (serum), if applicable	X ³								
Random (non-fasting) glucose		X						X	
AST/ALT	X				X	X	X	X	
Serum creatinine	X				X	X	X	X	
Cervical cultures ⁴	X								
MRI or Pelvic US ⁵	X								
D&C, LR-IUD insertion		X							
Pregnancy test (urine)	X ³								
Metformin Treatment ⁶									
AE Assessment									
Patient Diary			X			X ⁷		X	
Request tissue	X ⁸								
Endometrial Biopsy				X	X ⁹	X	X		
Blood and urine collection ¹⁰	X			X	X	X	X	X	

Metformin treatment begins D1 of Month 1; continue as per sections 4.3-4.4

Footnotes to Time and Events Table

¹Comprehensive medical history at baseline; thereafter history focused on symptoms and toxicities

²Patients will be followed until final study encounter, which will occur within 30 days of their final endometrial biopsy while on metformin. Metformin is to be stopped the day of the 12-month endometrial biopsy, or the day on which the results of prior biopsies are known, if they indicate disease progression. In the case of ongoing adverse events/serious adverse event, patients will be followed to resolution of the event. If early termination of the study occurs (i.e., prior to 12 months), the patient will be asked to have serum and urine collected, and the patient followed-up until any treatment related adverse events have resolved or returned to baseline. Their standard of care every 3 month (+/- 2 weeks) endometrial biopsy will be performed as scheduled by their physician as per routine care.

³Women of childbearing potential (WOCBP) must have negative urine pregnancy test within 7 days of D1 of treatment; urine pregnancy test (for WOCBP) will be conducted on the day of outpatient surgery as well, per standard of perioperative care.

⁴During the pelvic exam, which is part of the standard of care evaluation for newly diagnosed CAH/EC, cultures of gonorrhea and chlamydia will be taken to rule out cervical infection for women at high risk for sexually transmitted infections per ACOG recommendations. This includes women age 24 years or younger. Those women who have had negative gonorrhea or chlamydia testing or have been treated for gonorrhea or chlamydia within 3 months of placement do not require repeat cultures.

⁵For patients with EC only, MRI prior to the D&C is required to rule out >50% myometrial invasion or nodal metastases. Results of MRI studies of the uterus done within 30 days of enrollment will be accepted. For patients whose BMI precludes MRI testing, a pelvic ultrasound with tumor size measurements < 2 cm will be substituted.

⁶Treatment with metformin will last a minimum of 90 days and a maximum of 12 months depending on the patient's response to treatment as determined by endometrial biopsy.

⁷The first AE assessment will occur one week after starting metformin treatment; patients will be contacted weekly the first two weeks of therapy, and subsequently every 30 days by the study coordinator via phone to inquire about side effects of metformin. Adherence assessments will also be performed at the same intervals with patient reporting number of missed doses per week, based on review of their medication diary.

⁸Endometrial biopsy slides and blocks (pretreatment samples) will be obtained from referring physicians of these patients for analysis in this study

⁹At the 6 month timepoint only, an additional pass will be made with the endometrial pipele, in order to collect tissue for the correlative studies.

¹⁰For measurement of metformin concentration, and for metabolomics (see section 6.7).

6.2 Screening

Women with CAH/grade 1 endometrial cancer will be recruited from the Gynecologic Oncology and Gynecology clinics at participating centers. All patients will already have had a baseline endometrial biopsy performed, to establish their diagnosis and referral to the gynecologic oncology clinic. A sample of this tissue will be requested from the referring physician. All patients will have a urine pregnancy test (if of childbearing age), gonorrhea and chlamydia cervical cultures if they are age 24 or younger, and baseline serum creatinine, glucose and liver enzymes drawn at the time of their screening visit. These labs will be reviewed by the principal investigator. Note that screening labs must occur within 30 days of starting treatment.

6.3 Pre-Treatment

Per standard course of treatment, all women undergoing IUD placement for the treatment of CAH/EC will undergo dilation and curettage (D&C) procedure to confirm histologic diagnosis and for placement of the IUD if deemed necessary by their primary provider. Urine pregnancy test (for women of childbearing age) will be conducted on the day of outpatient surgery as well, per standard of perioperative care at UNC. Final pathology results from the D&C will be reviewed by the principal investigator. The patient will be notified within 3 days of the receipt of results, confirming CAH/grade 1 EC histology, that she is cleared to start study treatment with metformin. This will occur within 30 days of LR-IUD placement. Blood and urine samples will also be collected for correlative studies (see section 6.7). If the patient does not require a D&C, she will have a urine pregnancy test prior to IUD placement as is the standard of care and will start metformin within 30 days of IUD placement.

6.4 Treatment Assessments

6.4.1 Month 1 Week 1

D1 Month 1: Patient is instructed to initiate metformin via phone call: Patient will be contacted weekly for first 2 weeks by the study coordinator via phone regarding toxicities, and adherence assessments.

6.4.2 Monthly during Metformin

Patient will be contacted every 30 days by the study coordinator via phone regarding toxicities, and adherence assessments.

6.4.3 Months 3, 6, 9 and 12

Laboratory evaluations: serum creatinine, liver function test
Endometrial biopsy (see section 6.7)
Blood and urine samples for correlative studies (see section 6.7)
Random (non-fasting) glucose (month 12)

6.5 Final Study Encounter

Metformin is to be stopped the day of the 12-month endometrial biopsy, or the day on which the results of prior biopsies are known, if they indicate disease progression. In the case of ongoing adverse events/serious adverse event, patients will be followed to resolution of the event. After completion of metformin treatment, patients may return to clinic as per scheduled with their primary provider. The final study encounter will be within 30 days of the final endometrial biopsy.

6.6 Early Termination/Study Withdrawal Visit

If early termination of the study occurs (i.e., prior to 12 months), the patient will be asked to have serum and urine collected, and their standard of care every 3 month endometrial biopsy will be performed as scheduled by their physician as per routine care. No other evaluations will be needed in the event of early termination. Subjects may withdraw voluntarily from participation in the study at any time (see section 4.10). Subjects may also withdraw voluntarily from receiving the study intervention for any reason.

If voluntary withdrawal occurs due to an adverse event, the subject will be given appropriate care under medical supervision until the symptoms of any adverse event resolve or the subject's condition becomes stable.

6.7 Correlative Studies

Endometrial biopsies will be performed per standard clinical practices. At the first 6 month time point only, an additional pass will be made with the endometrial pipelle, in order to collect endometrial tissue for the correlative studies (i.e. measure metformin concentration and metabolomic profiling). The time at which the last dose of metformin was taken prior to endometrial biopsy will be recorded. Additionally, blood and urine samples will be collected from clinic and transported to the Tissue Procurement Facility for coding (to remove patient identifiers) and eventual distribution to the Principal Investigator. Samples will include: (1) a total of 10 cc of blood collected in a gold-top tube, (2) a total of 10 cc of blood collected in a green top heparinized tube, and (3) a minimum of 40 cc of urine collected in a non-sterile urine-specimen container. In addition, the endometrial biopsy slides and blocks (pretreatment samples) will be obtained from referring physicians of these patients for analysis in this study. These slides will also be compared to those obtained from serial endometrial biopsies, as a means to delineate the effect of metformin treatment. Tissue, blood and urine samples will be packaged and transported to the laboratory for determination of metformin concentration and metabolomic profiling.

Analysis of metformin in plasma and urine: Metformin concentrations in plasma and urine will be determined using a liquid chromatography–tandem mass spectrometry method in [name] laboratory.

Analysis of metformin uptake in endometrial tissue: Metformin concentrations in endometrial tissue will be determined using liquid chromatography-mass spectrometry (LC-MS/MS), as previously described (51). This will be performed in the laboratory of [name].

Ki-67: Tissue microarrays will be constructed and immunohistochemical analysis will be performed to assess for Ki-67. The percentage of Ki-67 positive cells, termed the Ki-67 index, will be calculated pre- and post-treatment. The Ki-max and Ki-min will also be quantified. Stained slides will be visually scored by experienced observers blinded to the identity of the tissue sections. Individual slides will be digitized using the Aperio ScanScope (Aperio Technologies, Vista, CA), and digital images will be analyzed using Aperio ImageScope software.

Immunohistochemical Analysis: Tissue microarrays will be constructed and immunohistochemical analysis will be performed to assess expression of the key components of the metformin/mTOR, including AMPK, LKB1, Akt, PTEN, S6K1 and 4E-BP1. Phosphorylated and non-phosphorylated forms of these proteins will be evaluated. Expression of the metformin transporter proteins will also be assessed by immunohistochemical analysis, including OCT1-3, MATE1/2 and PMAT. Stained slides will be visually scored by experienced observers blinded to the type of antibody used and to the identity of the tissue sections. Individual slides will be digitized using the Aperio ScanScope (Aperio Technologies, Vista, CA), and digital images will be analyzed using Aperio ImageScope software.

Metformin Transporter mRNA Expression in Endometrial Tissues. Total RNA will be isolated from EH paraffin-embedded tissues and subjected to RT-PCR for determination of metformin transporter mRNA expression, including OCT1-3, MATE1/2 and PMAT. The relative mRNA levels for individual transporters will be normalized to the 18s rRNA housekeeping gene.

Metabolomic Analysis: We will perform comprehensive metabolomic analysis of serum and urine to identify potential biomarkers responsive to metformin treatment using mass spectrometry. These analyses uncover the subtle differences between the spectra that correlate to the disease or treatment under study revealing metabolomic “footprints” (from tissue) and “fingerprints” (from biofluids). Thus, a comprehensive unbiased profiling of metabolites (molecule weight<1000 Dalton) will be performed, and we will analyze the metabolic “fingerprints” of the biofluids (i.e. serum and urine) of women with endometrial hyperplasia/cancer, pre- and post- 6 months of metformin treatment. Time of flight mass spectrometry (TOF-MS) coupled to chromatographic separations including gas chromatography (GC-TOF-MS, Leco Corp.) and liquid chromatography (LC-TOF-MS, Agilent Corp.) will be used for the measurement of tumor specimens and biofluids, and these analyses will be conducted according to previously developed methods by the UNC NORC/Nutrition Research Institute Metabolomics Core. Significant variables (metabolite markers) will be selected

based on a threshold of a multivariate statistical parameter, such as variable importance in the projection (VIP) value (usually $VIP > 1$) from a typical 7-fold cross-validated orthogonal projections to latent structures discriminant analysis (OPLS-DA) model. These differential metabolites will be validated at a univariate level such as Student's t-test and Wilcoxon-Mann-Whitney test. The critical p value of the test is usually set to 0.05.

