1.5 Correlative Studies

We will explore the association of metabolic factors, expression of the metformin transporter proteins and key targets of the metformin/mTOR signaling pathway (i.e. Ki-67, AMPK, LKB1, AKT, PTEN, S6, 4E-BP1) with treatment response to metformin. Metabolic factors, including baseline body mass index (BMI), and glucose levels, will be documented and followed throughout treatment. Matched paraffin embedded tissues before and during metformin treatment will also be collected for immunohistochemical analysis of the metformin transporter proteins, Ki-67, and key components of the metformin/mTOR signaling pathway. Blood and urine will be collected at baseline and every 3 months during the study as a

means to (1) explore associations between metformin concentration levels and therapeutic outcomes, and (2) identify metabolic biomarkers of response to treatment through metabolomic profiling. Endometrial tissue will also be collected at the 6 month time point for analysis of metformin uptake into the endometrium.

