2.3 Exploratory Objectives

- 2.3.1** To explore changes in cellular proliferation as measured by the marker, Ki-67, from baseline to 6 months
- 2.3.2** To explore association between the level of expression of the metformin transporter proteins and key targets of the metformin/mTOR signaling pathway and CR status at 6 months
- 2.3.3** To perform a comprehensive unbiased profiling of metabolites by analyzing the metabolic “fingerprints” of the biofluids (i.e. serum and urine) and “footprints” of the tumor tissue pre- and post- 6 months of metformin treatment
- 2.3.4** To explore association between metabolic factors and metformin concentration levels in tumor tissue/blood/urine and CR at 6 months

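### Section 6.7 ties no test to its pre/post metabolomic contrast, gives an independent-groups test as its nonparametric example, and states no false-discovery rate for the resulting list

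*Combined protocol and SAP*

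**What the plan says.** Section 6.7 (Metabolomic Analysis) sets the contrast as biofluids "pre- and post- 6 months of metformin treatment". Objective 2.3.3 adds the "tumor tissue pre- and post- 6 months of metformin treatment". Section 1.5 supplies the biofluid pairs: "Blood and urine will be collected at baseline and every 3 months during the study".

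Metabolites are first selected by VIP, usually above 1, "from a typical 7-fold cross-validated orthogonal projections to latent structures discriminant analysis (OPLS-DA) model". They are then "validated at a univariate level such as Student's t-test and Wilcoxon-Mann-Whitney test". Section 6.7 adds: "The critical p value of the test is usually set to 0.05".

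On measurement, 6.7 says "these analyses will be conducted according to previously developed methods" of the Metabolomics Core, and section 8.3 assigns all metabolomic analysis to that Core without naming a test or an error rate. For Ki-67 over the same interval, 8.3 names a paired t-test or the Wilcoxon signed-rank test.

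Tissue differs from serum and urine. Section 6.7 says "At the first 6 month time point only, an additional pass will be made with the endometrial pipelle"; the pretreatment tissue is slides and blocks from referring physicians.

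**The concern.** There are two separate points.

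1. **Test and contrast are not matched.** The contrast spelled out in 6.7 is within-woman. Wilcoxon-Mann-Whitney treats the two sets of samples as independent, so it ignores the pairing that repeat sampling provides. Whether Student's t-test would be run paired is not said.

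2. **The list has no stated error rate.** Metabolites picked by VIP are tested at 0.05 on what appear to be the same data. VIP>1 is a relative cutoff within the fitted model, so how many false hits it removes depends on the rest of the data. No false-discovery rate, permutation test, hold-out set or independent sample is stated. The 7-fold cross-validation assesses the model as a whole. No rule says the univariate step stops if the model fails, and cross-validation sets no per-metabolite error rate.

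What is at stake is how a reader should interpret the marker list under objective 2.3.3. The primary, secondary and safety analyses do not depend on it.

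**Working it through.** **The plan's own figures.** None is given for metabolomics. The only power figure is the primary one in 8.2 (30 patients, 50% versus 75%, two-sided 0.05, 80%). It reproduces: 21 or more responses of 30 gives power 0.803 and two-sided p 0.043. Only the 30 carries over here.

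**Assumptions not in the documents.** 500 metabolites; normal data; shifts of 0.5 or 0.8 SD; within-woman correlation ρ of 0.5 or 0.7, with 0 and 0.3 for range; 30 complete pairs, with 20 as a sensitivity case.

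**Step 1: pairing.** The paired t-test has noncentrality δ√n / √(2(1−ρ)).
- ρ = 0.5: 0.5 × √30 / √1.0 = 2.74 on 29 df, power 0.75.
- ρ = 0.7: 0.5 × √30 / √0.6 = 3.54, power 0.93.

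Mann-Whitney power was simulated (20,000 runs per cell):

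| ρ | Mann-Whitney | Paired t | Mann-Whitney size under no change |
|---|---|---|---|
| 0 | 45% | 46% | about 5% |
| 0.3 | 44% | 61% | about 2% |
| 0.5 | 44% | 75% | 0.7% |
| 0.7 | 44% | 93% | 0.1% |

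Repeat runs gave 42% to 44% for Mann-Whitney at ρ = 0.5 and 0.7. With 20 pairs the powers are 27% v 56% at 0.5 and 23% v 78% at 0.7. So the misapplied test loses power and is conservative; at ρ = 0 nothing is lost.

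**Step 2: false share of the list.** With no true change, a valid test gives 0.05 × 500 = 25 false hits. In simulation VIP>1 removed none of them (VIP = √M·|w|, with w the normalised first PLS-DA weight as a proxy for the OPLS-DA weight; no cross-validation step).

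With 25 true changes of 0.5 SD at ρ = 0.5 and a paired test, expected false hits are 0.05 × 475 = 23.75 and true hits 25 × 0.75 = 18.8. The share is 23.75 / 42.55 = 56%; the simulated mean share is 55%.

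Mean false share at ρ = 0.5 / 0.7:

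| True changes | Paired p<0.05 + VIP>1 | Mann-Whitney p<0.05 + VIP>1 |
|---|---|---|
| 25 at 0.5 SD | 55% / 51% | 23–24% / 4–5% |
| 50 at 0.5 SD | 37% / 32% | 13% / 2% |
| 100 at 0.8 SD | 12% / 5% | 3% / 0% |

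The paired column uses 300 simulated studies per cell. With a paired test, 100 true changes at 0.5 SD give 21% / 16%, and 150 at 0.8 SD give 4% / 1%. Under a global null, Mann-Whitney plus VIP>1 leaves 3.8 / 0.5 false hits instead of about 25. With uncorrelated pairs its protection disappears: 67% false for 25 true changes at 0.5 SD.

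VIP>1 does help when signal is broad and strong. With 100 true at 0.8 SD it cuts false hits from 20.1 to 13.6 (ρ = 0.5) and from 20.4 to 5.1 (ρ = 0.7).

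**Step 3: with a stated rate.** Benjamini-Hochberg q<0.10 on paired p values over all 500 metabolites holds the false share at 7–10% in every signal scenario (8–11% with 20 pairs).

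**Sensitivity of the paired p<0.05 + VIP>1 shares.** With 20 pairs: 63% / 54% for 25 at 0.5 SD, and 16% / 10% for 100 at 0.8 SD. With metabolites correlated 0.5 in blocks of 10 and 30 pairs: 55% / 50% and 12% / 5%.

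**The case against.** The strongest reply is that nothing here is fixed. The tests are offered as examples, the thresholds as usual values and the model as typical. Student's t-test can be run paired. Mann-Whitney would suit responders versus non-responders, and section 1.5 does look for biomarkers of response. The Core's methods may already include pairing and false-discovery control. All of this stands. A reader might infer that the plan commits to a wrong test; the wording does not support that. What remains is that 6.7 describes only the pre/post contrast, does not say which test goes with it, and cites no method that would settle the question.

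Second, the word *validated* is qualified: it is a check at a univariate level. Section 6.7 speaks of potential biomarkers and section 2.3 labels the objective exploratory. A reader might infer a claim of external validation; the text makes none. The label could still be plainer.

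Third, a reader might add the two faults together and expect a list that is both underpowered and mostly false. At clear positive correlation that does not happen: the high false shares arise with a paired test, while Mann-Whitney keeps false hits few and loses power instead.

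Fourth, q values are not uniformly better on false hits. With 100 true changes at 0.8 SD and ρ = 0.7, q<0.10 admits 9.0 false hits against 5.1 for paired p<0.05 plus VIP>1. The gain is a known rate, not always a smaller one.

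**Conclusion.** The point holds as a conditional one, confined to exploratory objective 2.3.3. Either Mann-Whitney is applied to the pairs, and power drops from about 75% to about 43% at ρ = 0.5 (30 pairs, 0.5 SD) with few false hits; or a paired test is used, and the false share is whatever the unknown number of true changes makes it: about 5% to 55% with 25 to 100 true changes at ρ = 0.5 or 0.7, lower still with 150 strong ones.

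It is tempting to conclude that most of the list would be false. The documents do not support that. They give no number of metabolites, effect size or correlation, and the earlier window study in section 1.3.2 reports lipid and carbohydrate shifts, so neither sparse nor broad signal can be assumed. The supportable statement is that a reader could not tell a list that is 5% false from one that is 50% false.

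This is a worthwhile minor improvement. Confidence in its size is moderate, because every magnitude rests on the assumptions listed and the simulation omits the cross-validation step.

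**What to change.** In section 6.7:

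- For the pre/post serum and urine contrast, name a paired t-test or Wilcoxon signed-rank test, as 8.3 does for Ki-67. Apply it to tissue only where usable pre/post pairs exist.
- Keep two-sample tests for CR versus non-CR.
- Report p values, Benjamini-Hochberg q values and VIP side by side, with q computed over all measured metabolites and not only those with VIP>1. Any cutoff should be set by the sponsor in advance.
- Describe the list as hypothesis-generating unless independent data are used.
- If the Core's methods already do this, cite them instead.

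The change is wording only; samples and software stay the same. The downside is a shorter flagged list if a q cutoff is used when effects are sparse and modest. With 25 true changes at 0.5 SD, q<0.10 keeps 6.2 true changes against 18.8 for paired p<0.05 plus VIP>1 at ρ = 0.5, and 15.8 against 23.1 at ρ = 0.7. With 20 pairs the figures are 1.7 against 13.9 and 6.8 against 19.7. A looser q<0.20 keeps 9.9 of 25 at ρ = 0.5 (30 pairs), with 18% of the list false. With 100 true changes at 0.8 SD almost nothing is lost (97.1 against 98.6 at ρ = 0.5). Reporting p and q for every metabolite keeps the unflagged ones visible.
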